#### 10.1.2. Reporting Procedure

All events (serious and non-serious) must be reported with investigator's assessment of the event's seriousness, severity, and causality to the blinded study drug. For SAEs and AESIs, a detailed narrative summarizing the course of the event, including its evaluation, treatment, and outcome should be provided on the AE case report form (CRF). Specific or estimated dates of event onset, treatment, and resolution should be included, when available. Medical history, concomitant medications, and laboratory data that are relevant to the event should also be summarized in the narrative. For fatal events, the narrative should state whether an autopsy was or will be performed, and include the results if available. Information not available at the time of the initial report must be documented in a follow-up report. Source documents (including hospital or medical records, diagnostic reports, etc) will be summarized in the narrative on the AE CRF, and retained at the study center and available upon request.

Urgent safety queries must be followed up and addressed promptly. Follow-up information and response to non-urgent safety queries should be combined for reporting to provide the most complete data possible within each follow-up.

# 10.1.3. Events that Require Expedited Reporting to Sponsor

The following events also require reporting to the sponsor (or designee) within 24 hours of learning of the event:

- SAEs
- Selected Adverse Events of Special Interest (AESI; serious and nonserious): Adverse events of special interest for this study include the following:
  - Severe or systemic hypersensitivity reactions
     NOTE: Anaphylaxis will be prospectively analyzed using the criteria discussed in the statement paper from the Second Symposium on the definition and Management of Anaphylaxis (Sampson, 2006)
  - Asthma exacerbations, defined as asthma symptoms requiring treatment with systemic corticosteroids or resulting in an emergency room visit or hospitalization
- **Pregnancy:** Although pregnancy is not considered an AE, it is the responsibility of the investigator to report to the sponsor (or designee), within 24 hours of identification,

any pregnancy occurring in a female during the study or within 24 weeks of the last dose of study drug. Any complication of pregnancy affecting a female study patient, and/or fetus and/or newborn that meets the SAE criteria must be reported as an SAE. Outcome for all pregnancies should be reported to the sponsor.

## 10.2. **Definitions**

#### 10.2.1. Adverse Event

An AE is any untoward medical occurrence in a patient administered a study drug which may or may not have a causal relationship with the study drug. Therefore, an AE is any unfavorable and unintended sign (including abnormal laboratory finding), symptom, or disease which is temporally associated with the use of a study drug, whether or not considered related to the study drug (ICH E2A Guideline. Clinical Safety Data Management: Definitions and Standards for Expedited Reporting, Oct 1994).

#### **10.2.2.** Serious Adverse Event

An SAE is any untoward medical occurrence that at any dose:

- Results in **death** includes all deaths, even those that appear to be completely unrelated to study drug (eg, a car accident in which a patient is a passenger).
- Is **life-threatening** in the view of the investigator, the patient is at immediate risk of death at the time of the event. This does not include an AE that had it occurred in a more severe form, might have caused death.
- Requires in-patient **hospitalization** or **prolongation of existing hospitalization**. In-patient hospitalization is defined as a hospital admission (any duration) or an emergency room visit for longer than 24 hours. Prolongation of existing hospitalization is defined as a hospital stay that is longer than was originally anticipated for the event, or is prolonged due to the development of a new AE as determined by the investigator or treating physician.
- Results in persistent or significant **disability/incapacity** (substantial disruption of one's ability to conduct normal life functions).
- Is a congenital anomaly/birth defect
- Is an **important medical event** Important medical events may not be immediately life-threatening or result in death or hospitalization, but may jeopardize the patient or may require intervention to prevent one of the other serious outcomes listed above (eg, intensive treatment in an emergency room or at home for allergic bronchospasm; blood dyscrasias or convulsions that do not result in hospitalization; or development of drug dependency or drug abuse).

Criteria for reporting SAEs must be followed for these events.

## **10.2.3.** Adverse Events of Special Interest

An adverse event of special interest (AESI; serious or non-serious) is one of scientific and medical interest specific to the sponsor's product or program, for which ongoing monitoring and rapid communication by the investigator to the sponsor can be appropriate. Such an event might warrant further investigation in order to characterize and understand it.

#### **10.2.4.** Severity

The severity of AEs will be graded according to the following scale:

**Mild:** Does not interfere in a significant manner with the patient's normal functioning level. It may be an annoyance. Prescription drugs are not ordinarily needed for relief of symptoms, but may be given because of personality of the patient.

**Moderate:** Produces some impairment of functioning but is not hazardous to health. It is uncomfortable or an embarrassment. Treatment for symptom may be needed.

**Severe:** Produces significant impairment of functioning or incapacitation and is a definite hazard to the patient's health. Treatment for symptom may be given and/or patient hospitalized.

If a laboratory value is considered an AE, its severity should be based on the degree of physiological impairment the value indicates.

## **Injection Site Reactions**

The severity of injection site reactions will be graded according to the following scale (semi-colon indicates "or" within description of grade:

**Mild**: Pain that does not interfere with activity; mild discomfort to touch; <5 cm of erythema or induration that does not interfere with activity

**Moderate**: Pain that requires repeated use of non-narcotic pain reliever >24 hours or interferes with activity; discomfort with movement; 5.1 cm to 10 cm erythema or induration or induration that interferes with activity

**Severe**: Pain that requires any use of narcotic pain reliever or that prevents daily activity; significant discomfort at rest; >10 cm erythema or induration; prevents daily activity; requires emergency room visit or hospitalization; necrosis or exfoliative dermatitis

#### 10.2.5. Causality

The investigator must provide causality assessment as to whether or not there is a reasonable possibility that the drug caused the AE, based on evidence or facts, his/her clinical judgment, and the following definitions. The causality assessment must be made based on the available information and can be updated as new information becomes available.

For double blinded studies using an active comparator, the investigator should consider all study drugs in determining event causality.

The following factors should be considered when assessing causality:

- Temporal relationship: time to onset versus time drug was administered
- Nature of the reactions: immediate versus long term

- Clinical and pathological features of the events
- Existing information about the drug and same class of drugs
- Concomitant medications
- Underlying and concurrent illnesses
- Response to dechallenge (drug discontinuation) or dose reduction
- Response to rechallenge (re-introduction of the drug) or dose increase, when applicable
- Patient's medical and social history

Causality to the study drug (including study drug administration):

#### • Related:

 The AE follows a reasonable temporal sequence from study drug administration, and cannot be reasonably explained by the nature of the reaction, patient's clinical state (eg, disease under study, concurrent diseases, concomitant medications), or other external factors.

or

 The AE follows a reasonable temporal sequence from study drug administration, and is a known reaction to the drug under study or its class of drugs, or is predicted by known pharmacology.

#### • Not Related:

 The AE does not follow a reasonable sequence from study drug administration, or can be reasonably explained by the nature of the reaction, patient's clinical state (eg, disease under study, concurrent diseases, and concomitant medications) or other external factors.

Causality to the study conduct (protocol specified procedure):

#### • Related:

The AE follows a reasonable temporal sequence from a protocol specified procedure, and cannot be reasonably explained by the nature of the reaction, patient's clinical state (eg, disease under study, concurrent diseases, concomitant medications), or other external factors.

#### Not Related:

 The AE does not follow a reasonable sequence from a protocol specified procedure, or can be reasonably explained by the nature of the reaction, patient's clinical state (eg, disease under study, concurrent diseases, and concomitant medications) or other external factors.

# **10.3.** Safety Monitoring

The investigator will monitor the safety of study patient at his/her site(s) as per the requirements of this protocol and consistent with current Good Clinical Practice (GCP). Any questions or concerns should be discussed with the sponsor in a timely fashion. The sponsor will monitor the safety data from across all study sites. The Medical/Study Director will have primary responsibility for the emerging safety profile of the compound, but will be supported by other departments (eg, Global Patient Safety (GPS); Biostatistics and Data Management). Safety monitoring will be performed on an ongoing basis (eg, individual review of SAEs) and on a periodic cumulative aggregate basis.

# 10.4. Notifying Health Authorities, Institutional Review Board/Ethics Committee, and Investigators

During the study, the sponsor and/or the CRO will inform health authorities, Institutional Review Boards (IRBs)/Ethics Committees (ECs), and the participating investigators of any Suspected Unexpected Serious Adverse Reactions (SUSARs) occurring in other study centers or other studies of the active study drug (REGN1908-1909), as appropriate per local reporting requirements. In addition, the sponsor and/or CRO will comply with any additional local safety reporting requirements. All notifications to investigators will contain only blinded information.

Upon receipt of the sponsor's notification of a SUSAR that occurred with the study drug, the investigator will inform the IRB/EC unless delegated to the sponsor.

Event expectedness for study drug (REGN1908-1909) is assessed against the Reference Safety Information section of the Investigator's Brochure that is effective for expedited safety reporting.

At the completion of the study, the sponsor will report all safety observations made during the conduct of the trial in the Clinical Study Report to health authorities and IRB/EC as appropriate.

#### 11. STATISTICAL PLAN

This section provides the basis for the statistical analysis plan (SAP) for the study. The SAP will be revised prior to the end of the study to accommodate amendments to the clinical study protocol and to make changes to adapt to unexpected issues in study execution and data that may affect the planned analyses. The final SAP will be issued before the first database lock.

Endpoints are listed in Section 4. Analysis variables are listed in Section 5.

Handling of missing data due to the COVID-19 pandemic and any additional analyses required to investigate the impact of COVID-19 to understand estimated treatment effect and safety will be detailed in the SAP.

# 11.1. Statistical Hypothesis

For comparison of REGN1908-1909 to placebo, the following hypothesis of the primary endpoint (the average daily CSMS over the last 12 weeks of the treatment period [weeks 48 to 60]) will be tested:

H0: There is no difference in CSMS, averaged over the last 12 weeks of the treatment period (weeks 48 to 60), in patients receiving REGN1908-1909 and placebo.

H1: The CSMS, averaged over the last 12 weeks of the treatment period (weeks 48 to 60, is significantly different in patients receiving REGN1908-1909 and placebo.

The statistical hypothesis specified above can be tested on the selected secondary endpoints. The study will be declared positive if at least the null hypothesis for the primary efficacy endpoint for REGN1908-1909 versus placebo is rejected.

# 11.2. Justification of Sample Size

The sample size will be approximately 315 patients per arm, for a total of 630 patients. This study is powered to detect the difference between REGN1908-1909 and placebo on the primary endpoint of daily CSMS averaged over the last 12 weeks of the treatment period (weeks 48 to 60) when considering a 20% dropout rate by week 60.

A sample size of 251 patients per arm gives 90% power to detect a mean difference in daily average CSMS of 1.8 (20% reduction from placebo) between REGN1908-1909 (mean CSMS=7.3) and placebo (mean CSMS=9.1), assuming a common standard deviation in CSMS of 6.2. Assuming a 20% dropout rate (~64 per arm), the sample size is 315 per arm. A 2-sample t-test with 2-sided alpha of 0.05 was assumed. Calculations were performed using nQuery+nTerim 4.0

The sample size of 315 patients per arm also gives the power of 91% and 96% to detect a 20% reduction from placebo in TSS (SD=3.0 and mean in placebo=4.2) and daily TNSS (SD=2.3 and mean in placebo=3.3) averaged over the last 12 weeks (weeks 48 to 60), respectively. Details are displayed in Table 4.

The assumptions of mean in the placebo and common standard deviation for the above endpoints are based on the house dust mite (HDM) SLIT-tablet data (Demoly, 2016) for combined rhinoconjunctivitis score during 8-week assessment period. A treatment difference of 20% relative to placebo is based on a previous phase 1b study (R1908-1909-ALG-1325) of the same molecules

and the treatment effect observed for reduction in symptoms after a nasal allergen challenge over a 12-week period.

Table 4: Summary of Statistical Assumptions and Power for Selected Secondary Endpoints

Daily Score,	Mean		Anti-Fel d		
Averaged over 12 weeks	РВО	Anti-Fel d 1	% Reduction from PBO	Reduction from PBO (SD)	Power with n=315/arm
TNSS	3.3	2.6	-20%	-0.7 (2.3)	96%
TSS	4.2	3.4	-20%	-0.8 (3.0)	91%

The sample size may be re-estimated in a blinded fashion after greater than 50% of patients have baseline data available using observed values of CSMS to determine the baseline PBO mean (SD) and assuming the same 20% difference between REGN1908-1909 versus placebo. If the re-estimated number is higher than the current estimation of 315 per arm, then the sample size may be increased.

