#### **Statistical Plan**

# **Justification of Sample Size**

The sample size will be approximately 315 patients per arm, for a total of 630 patients. This study is powered to detect differences between REGN1908-1909 and placebo on the primary endpoint of daily average CSMS averaged over the last 12 weeks of the treatment period (weeks 48 to 60 primary) when considering a 20% dropout rate by week 60.

A sample size of 251 patients per arm gives 90% power to detect a mean difference in daily average CSMS of 1.8 (20% reduction from placebo) between REGN1908-1909 (mean CSMS = 7.3) and placebo (mean CSMS = 9.1), assuming a common standard deviation in CSMS of 6.2. Assuming a 20% dropout rate (~64 per arm) by the last 12 weeks (weeks 48 to 60), the sample size is 315 patients per arm. A 2-sample t-test with 2-sided alpha of 0.05 was assumed. Calculations were performed using nQuery+nTerim 4.0.

A sample size of 315 patients per arm also gives the power of 91% and 96% to detect a 20% reduction from placebo in TSS (SD=3.0 and mean in placebo=4.2) and TNSS (SD=2.3 and mean in placebo=3.3) during the primary efficacy period, respectively.

Estimates of mean in the placebo and common variability are based on the house dust mite (HDM) SLIT-tablet data for combined rhinoconjunctivitis score during 8-week assessment period. A treatment difference of 20% relative to placebo is based on a previous phase 1b study (R1908-1909-ALG-1325) of the same molecules and the treatment effect observed for reduction in symptoms after a nasal allergen challenge over a 12-week period.

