2.3. Sample Size and Power Considerations

The sample size will be approximately 315 patients per arm, for a total of 630 patients in two treatment groups. This study is powered to detect the difference between REGN1908-1909 and placebo on the primary endpoint of daily CSMS averaged over the last 12 weeks of the treatment period (weeks 48 to 60) when considering a 20% dropout rate by week 60.

A sample size of 251 patients per arm gives 90% power to detect a mean difference in daily CSMS, averaged over weeks 48-60, of 1.8 (20% reduction from placebo) between REGN1908-1909 (mean CSMS=7.3) and placebo (mean CSMS=9.1), assuming a common standard deviation in CSMS of 6.2. Assuming a 20% dropout rate (~64 per arm), the sample size is 315 per arm. A 2-sample t-test with 2-sided alpha of 0.049 was assumed (an administrative penalty of 0.001 will be taken from the significance level used at final analysis due to a planned interim analysis; details are provided in Section 7). Calculations were performed using nQuery+nTerim 4.0.

The sample size of 315 patients per arm also gives the power of 91% and 96% to detect a 20% reduction from placebo in TSS (SD=3.0 and mean in placebo=4.2) and daily TNSS (SD=2.3 and mean in placebo=3.3) averaged over the last 12 weeks (weeks 48 to 60), respectively. Details are displayed in Table 1.

Table 1: Summary of Statistical Assumptions and Power for Select Secondary Endpoints

Daily Score, Averaged over last 12 weeks	Mean		Anti-Fel d 1 vs Placebo		Power with n=315/arm*	Power with n=251/arm*
	Placebo	Anti-Fel d 1	% Reduction from Placebo	Reduction from Placebo (SD)		
TNSS	3.3	2.6	-20%	-0.7 (2.3)	96%	92%
TSS	4.2	3.4	-20%	-0.8 (3.0)	91%	84%

*: Two-sided t-test with alpha = 0.049, assuming 20% reduction from PBO

The assumptions of mean in the placebo and common standard deviation for the above endpoints are based on the house dust mite (HDM) SLIT-tablet data for combined rhinoconjunctivitis score during 8-week assessment period. A treatment difference of 20% relative to placebo is based on a previous phase 1b study (R1908-1909-ALG-1325) of the same molecules and the treatment effect observed for reduction in symptoms after a nasal allergen challenge over a 12-week period.

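### Power for TSS and TNSS at weeks 48 to 60 is stated at 315 per arm with no dropout, while primary CSMS power uses 251 per arm after 20% dropout

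*Protocol*

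**What the plan says.** Protocol 11.2 builds the primary sample size in two steps. First, "A sample size of 251 patients per arm gives 90% power to detect a mean difference in daily average CSMS of 1.8" against placebo, "assuming a common standard deviation in CSMS of 6.2". Then it inflates for loss: "Assuming a 20% dropout rate (~64 per arm), the sample size is 315 per arm". The test is given as "A 2-sample t-test with 2-sided alpha of 0.05 was assumed"; SAP 2.3 uses 0.049 instead.

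The next paragraph turns to two secondary endpoints over the same weeks 48 to 60: "The sample size of 315 patients per arm also gives the power of 91% and 96" percent, for TSS (placebo mean 4.2, SD 3.0) and TNSS (placebo mean 3.3, SD 2.3). Protocol Table 4 gives the same powers under a column for 315 per arm, with differences of 0.7 for TNSS and 0.8 for TSS. The synopsis repeats the statement.

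SAP 2.3 repeats the sentence, but its Table 1 adds a column at 251 per arm: 92% for TNSS and 84% for TSS. SAP 10.6 tabulates TNSS power at the planned sample size, which its footnote defines as 251 per arm (315 enrolled less 20% dropout). It shows 89%, using a difference of 0.66.

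**The concern.** CSMS is TSS plus the medication score, and TSS is TNSS plus the ocular score. All come from the same nightly e-diary in the same patients. A patient who contributes no diary data in weeks 48 to 60 contributes to none of the three, so dropout cannot apply to CSMS and spare its components. Yet the protocol gives post-dropout power for the primary endpoint and no-dropout power for the two secondaries, without saying that the basis has changed.

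A reader of the protocol alone would conclude that TSS and TNSS both have more power than the primary endpoint. On a common basis, TSS has less than the primary in every variant, and TNSS has slightly more or slightly less depending on the difference used. In SAP 5.6.3, TNSS is second and TSS seventh in the fixed testing order, so these figures inform expectations about the hierarchy.

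**Working it through.** **Inputs.** n per arm 315 and 251; dropout 20%; CSMS difference 1.8, SD 6.2; TNSS difference 0.7, SD 2.3; TSS difference 0.8, SD 3.0 (Protocol 11.2 and Table 4). Exact 20% reductions are 0.20 × 3.3 = 0.66 for TNSS and 0.20 × 4.2 = 0.84 for TSS. Two-sided alpha is 0.05 (Protocol) or 0.049 (SAP), with 1:1 allocation.

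**Formula.** Power ≈ Φ(δ/SD × √(n/2) − z), with z = 1.960 at alpha 0.05. The table uses the exact noncentral-t version; the two agree to within about 0.15 of a percentage point. √(315/2) = 12.550 and √(251/2) = 11.203.

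**Primary, reproduced.** 1.8/6.2 × 11.203 = 3.252; Φ(3.252 − 1.960) = 0.902. The exact t-test gives 90.1%. Inflation: 251/0.80 = 313.75, so 314, against the planned 315; and 315 − 251 = 64, as stated.

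**Secondary at 315, reproduced.**
- TNSS: 0.7/2.3 × 12.550 = 3.820; Φ(1.860) = 0.969 (stated 96%).
- TSS: 0.8/3.0 × 12.550 = 3.347; Φ(1.387) = 0.917 (stated 91%).

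Both agree with the stated figures within one point, which confirms that no dropout is included.

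**Secondary at 251.**
- TNSS: 0.7/2.3 × 11.203 = 3.410; Φ(1.450) = 0.926.
- TSS: 0.8/3.0 × 11.203 = 2.987; Φ(1.027) = 0.848.

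**All variants, exact t-test power (%).**

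| Endpoint, difference | n=315, α 0.05 | n=315, α 0.049 | n=251, α 0.05 | n=251, α 0.049 |
|---|---|---|---|---|
| TNSS, 0.7 (tabulated) | 96.81 | 96.75 | 92.55 | 92.43 |
| TNSS, 0.66 (exact 20%) | 94.91 | 94.81 | 89.41 | 89.25 |
| TSS, 0.8 (tabulated) | 91.64 | 91.51 | 84.65 | 84.45 |
| TSS, 0.84 (exact 20%) | 93.93 | 93.82 | 87.92 | 87.74 |

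Three things follow.
- Choosing alpha 0.05 or 0.049 moves power by at most about 0.2 points, so it does not explain the gap.
- The tabulated differences are rounded, down for TSS and up for TNSS. With them, the 251-per-arm power is about 4 points (TNSS) and 7 points (TSS) below the stated figures. With exact 20% reductions the shortfalls are about 7 and 3 points.
- SAP Table 1 (92%) and SAP 10.6 (89%) disagree for TNSS at the same 251 per arm and alpha 0.049 only because one uses 0.7 and the other 0.66.

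**The case against.** The strongest reply is that no printed figure is wrong. The sentence and the Table 4 column both name 315 per arm, and at that n the figures reproduce. That stands: this is a mismatch of basis, not a calculation error.

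Second, the SAP already publishes the post-dropout powers in Table 1. That stands too and largely cures the problem for a SAP reader. It does not reach Protocol 11.2, Table 4 or the synopsis, and the SAP 2.3 sentence still leads with the 315 figures.

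Third, 251 may understate the information available. The full analysis set keeps everyone randomised, data after stopping study drug are used, a patient who leaves partway through weeks 48 to 60 still contributes observed days, and the ANCOVA adjusts for baseline. The effective n could therefore lie somewhat above 251. This is fair, but imputing an average does not restore a lost observation, and the documents quantify none of it. Their own power method takes no credit for it, either for CSMS or in SAP 10.6.

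A reader might infer that the design is underpowered, that the sample size should rise, or that the testing hierarchy is compromised. The documents do not support this. The study is powered on CSMS, and that calculation already carries the dropout. No power target is set for TSS or TNSS. TSS is tested only after six earlier successes, so its marginal power says little about how far testing will run.

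**Conclusion.** The point holds as a minor inconsistency in how secondary power is stated. The 91% and 96% describe a trial with complete retention. On the plan's own post-dropout basis, power is about 92% (TNSS) and 84-85% (TSS) with the tabulated differences, or about 89% and 88% with exact 20% reductions. TSS is below 90% either way; TNSS is above or below depending on which difference is meant.

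These results rest on the plan's means, SDs and 20% dropout, on a two-sample t-test, and on counting dropouts as contributing nothing, as the plan does for CSMS. Credit for partial diaries, imputation or baseline adjustment could raise them somewhat. Primary power, the total of 630, alpha and the testing order do not change.

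**What to change.** In Protocol 11.2, Table 4 and the synopsis, and in the SAP 2.3 sentence, give the 251-per-arm figures as the design power for TSS and TNSS. Alternatively, keep 91% and 96% labelled as assuming no dropout and print the 251-per-arm figures beside them.

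First settle one difference per endpoint, because copying 92% and 84% across would leave the protocol in conflict with the 89% in SAP 10.6.
- If the tabulated 0.7 and 0.8 are kept, the design figures are about 92% and 84-85%, and the TNSS rows of SAP 10.6 need recalculating at 0.7.
- If exact 20% reductions (0.66 and 0.84) are used, the design figures are about 89% and 88%. The 315-per-arm figures then become about 95% and 94%, and Protocol Table 4 and SAP Table 1 change to match.

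The cost is a few sentences and table cells, and a less favourable secondary power statement. No change to sample size or analysis is needed.
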